**Figure 3: Injection Sites for Phase 2A Study**

#### RZL-012-P2aUS-001.4 Study Results:

In this study, in which significantly higher doses were tested (up to 180 mg), RZL-012 was found to be safe in all cohorts. There were no clinically significant changes in vital signs, ECG and all blood laboratory parameter. The most commonly reported AEs for which there seemed to be a causal relationship to active treatment, due to the higher incidence in the active treatment groups compared to the placebo groups, were injection site pain and injection site edema. Most AEs were transient. There was only a single case in the highest injected dose, Cohort 4, where erythema and edema were still observed up to Day 140.

The only systemic effect due to the subcutaneous injection of RZL-012 was elevation in d-dimer values at the highest injected dose of 180 mg. However, this increase was transient, up to 3 days after injection, and non-clinically significant. Further review of coagulation parameters revealed there was no clinically significant activation of the coagulation system nor any presence of Disseminated Intravascular Coagulation (DIC). The absence of any clinical symptoms related to elevation of D-dimer supports a direct link between RZL-012 induced inflammation and elevated D-dimer levels, unrelated to venous thromboembolic disease.

Biopsies taken from two injection sites revealed no damage to the skin 56 days following RZL-012 injection. Based on the histology results, the process that seemed to be dominant is fat necrosis and infiltration of macrophages into the necrotic fat tissue that resulted in a replacement of the local fat tissue by fibrotic tissue.

A decrease from baseline in SFM ratio (injected/non-injected side), as assessed by MRI, was noted in RZL-012 treated subjects of Cohorts 2 – 4 at all study time points. In addition, a dose dependent response was evident and statistically significant differences in SFM were found in RZL-012 treatment groups versus placebo. Among Cohorts 4 subjects who were monitored until 168 days post injection, a clear reduction in SFM was noticed (-14.32%). Cohort 4 subjects demonstrated the largest reduction in SFM at Day 56 (-18.10%).

There were no major changes over time and no specific trend to suggest a dose correlation response in any of the parameters of lipid profile (TC, TG, LDL, HDL, and FFA) and fasting glucose.

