**Figure 6: Diagram of Injection Pattern**

Subjects were injected with RZL-012 or vehicle perpendicularly (90°) to the skin. An ice pack was placed on the injected area for pain relief immediately after injection. Subjects had to remain seated in the injection position for an additional 10 minutes after dosing.

RZL-012-SMF-P2a-US-001 Results:

AEs were closely followed up throughout the study to determine the safety profile of RZL-012. Different scales were used to grade the severity degree of edema and erythema, pain, bruising and induration. Most of AEs were treatment related.

The most commonly reported AEs were bruising, induration, edema, pain and erythema all of which were reported with a similar incidence in the RZL-012 and placebo treatment groups. A difference was evident in the severity of some of the AEs in the RZL-012 high-dose treatment group vs. placebo with 3 reports by 3 subjects of severe edema and 2 reports by 2 subjects of severe induration in the high dose group. However, these AEs were characterized as such only within the first 24 hours of administration. The intensity then went from moderate to mild in the days following the RZL-012 injection and were completely resolved by 56 days after injection without any specific treatment or medication. Erythema, and bruising were not dose related and were mostly resolved at 14 days after injection. There were no clinically significant changes in vital signs, no deaths and no SAEs in any subjects.

Based on the objective MRI, it can be concluded that the efficacy of RZL-012 in reducing SMF in this Phase 2a study was demonstrated. This is evident by both the change in the submental depth (thickness) as well as volume. The robustness of these results is supported by the dose response that shows larger effects for the higher dose of RZL, i.e., a volume reduction of -22.2% $\pm$ 14.9 vs. Volume reduction of -10.6% $\pm$ 14.5 and -0.4% $\pm$ 13.9 for RZL-012 low dose and placebo, respectively.

The objective MRI assessments were supported by the Physician Impression scale. This scale which shows a more pronounced improvement at days 56 and 84 compared to day 28 may indicate that the effects of RZL-012 on SMF progress and cumulate in the weeks following the administration of the product. All besides 1 of the 18 RZL-012-treated subjects demonstrated improvement in SMF at 84 days after treatment. On the other hand, at Day 84, none of the placebo subjects demonstrated any change in their SMF.

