### **5.0 SAFETY ASSESSMENTS**

#### **5.1 Collection of Adverse Events Data**

Data regarding treatment-emergent AEs (TEAEs) will be collected in this study. TEAEs are events that are not present at baseline, or if present at baseline, have worsened in severity. AEs will be assessed while the subjects are in the study. AEs assessed by the Investigator as related to study drug and “ongoing” at discharge will be monitored by the Investigator until resolved or until the subject is deemed “lost to follow-up”.

Any AEs reported by the subject or noted by the Investigator or his/her designee will be recorded on the eCRF regardless of the Investigator opinion of causality. The following information will be recorded for each AE: description of the event, date and time of onset, date and time of

resolution, severity, causal relationship to study drug, outcome, action taken with the study drug and any treatment given.

The AEs reported during the trial will be graded, documented, and assessed in regards to their clinical significance and relation to study drug. Treatment area evaluations including, but not limited to evaluation of edema, bruising, dysphasia, dysphonia, erythema, dyspigmentation, induration, numbness, pain, paresthesia, pruritus, skin ulceration and necrosis, injury to the marginal mandibular nerve, vascular and nerve injury and tissue damage to nearby vulnerable anatomic structures..

All abnormal changes from baseline will be collected, graded with regards to severity or clinical significance, assessed for causal relationship and recorded on the eCRF.

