### **11.2.4 Internal Safety Committee**

An internal safety review committee will review the safety data collected during the study in a blinded manner. The committee members will include study medical monitor, Raziel's CMO and clinical director.

The meeting will be held when every enrolled 40 subjects completed Day 7. Summary of the safety including all subjects up to that point may be reviewed as well. Following completion of enrollment of all subjects, the committee will meet quarterly during the follow up period.

The study enrollment will be suspended if either of the following occur:

- Greater than 20% of subjects report a drug related grade 3 (severe) adverse event for a period duration of more than 28 days after injection. Of note severe swelling is may be during the first 24 – 96 hours after injection.
- >1 subject with a drug related CTCAE Grade of 4 or 5

In the event of the above, the enrollment and treatment will be suspended, the safety committee will review all data to examine potential safety issue. Additional experts may be brought in to review safety data if deemed necessary by the safety committee. A safety report will be issued with the conclusions of the meeting. The recommendation of the safety committee will be documented. Potential outcomes are reinitiating enrollment with current safety practices, reinitiating study with caveats (e.g. additional precautions/limitations or safety training), stop enrollment.. For each internal safety committee meeting, report will be prepared by the medical monitor that include data about enrollment, list of SAEs, summary of AEs.

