## 12.4 Safety

Safety data will be summarized by dose group and based on their initial dose level or treatment group (i.e., if a dose reduction occurs, they will be considered in their initial group). Descriptive statistics will be provided for actual values and change from baseline values for vital signs, weight, blood parameters, ECG (QT).

AE assessment and treatment area evaluation including, but not limited to evaluation of edema, bruising, dysphasia, dysphonia, erythema, dyspigmentation, induration, numbness, pain, paresthesia, and pruritus.

The incidence and severity of AEs reported during the study and their relationship to study drug will be tabulated. AEs will be coded using MedDRA™ and will be presented by body system. AEs will be graded according to the Common Terminology Criteria for Adverse Events (CTCAE) v 5.0 (Table 5).

The World Health Organization Drug Dictionary (WHODD) will be used to classify prior and concomitant medications by therapeutic class and preferred term. Prior and concomitant medication usage will be summarized by the number and percentage of subjects receiving each medication within each therapeutic class by dose cohort.

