## 6. STATISTICAL ANALYSIS

- General

All measured variables and derived parameters will be listed individually and, if appropriate, tabulated by descriptive statistics.

For categorical variables, summary tables will be provided giving sample size, absolute and relative frequency and 95% CI (Confidence Interval) for proportions by study group.

For continuous variables, summary tables will be provided giving sample size, arithmetic mean, standard deviation, coefficient of variation (CV%), median, minimum and maximum and 95% CI (Confidence Interval) for means of variables by study group.

All tests will be two-tailed, and a p value of 5% or less will be considered statistically significant.

The data will be analyzed using the SAS ® version 9.4 (SAS Institute, Cary North Carolina).

Statistical methods presented in the SAP may be slightly different from those that are presented in the protocol. Differences are clearly stated and the SAP supersedes the protocol only with regard to the way data will be handled and analysed.

- Subject Disposition

A detailed description of subject accountability including count of subjects included, exposed, completed (i.e., subjects who complete the study treatment) and discontinued along with the main reason for discontinuation will be generated for each treatment group and for all subjects. All withdrawals from the study, taking place on or after study drug injection, will be fully documented in the body of the Clinical Study Report.

Demographic and Baseline Characteristics

MediStat Statistics in Medicine	DOCUMENT NUMBER: 140-BST-PLN-001	PAGE: 14 of 16
TITLE: Statistical Analysis Plan of Protocol Number RZL-012-SMF-P2bUS-001	EFFECTIVE DATE : 08/03/2022 REVISION NUMBER : 1.0	

Baseline will be defined as the last available and evaluable parameter value before and closest to the injection. If a rechecked value is used for baseline, it should be collected under the same conditions as for the planned baseline.

Baseline safety data will be presented along with subsequent safety values assessed during or after dosing.

- **Analysis of Efficacy for Primary Endpoint**

The proportion of subjects who have at least a 1-grade improvement in the C-CAT on Day 84 versus baseline will be calculated for the placebo group and the RZL-012 high-dose group along with 95% Confidence interval for proportion.

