Safety data from the study will be summarized descriptively by treatment. The incidence of AEs will be presented by treatment.

Descriptive statistics will be calculated for quantitative data and frequency counts and percentages will be provided for categorical data. The nature, frequency, seriousness, severity and relation of AEs to study treatment will be tabulated for all subjects combined and by treatment.

Change-from-baseline values for vital signs, clinical laboratory and ECG will be summarized. Serious adverse events (SAEs) will be described in narratives as part of the study report.

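### The planned adverse-event tables leave out duration and resolution, so a difference between arms in how long local reactions last may go unseen

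*SAP*

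**What the plan says.** SAP section 6, Analysis of Safety, makes two commitments on adverse events: "The incidence of AEs will be presented by treatment", and "The nature, frequency, seriousness, severity and relation of AEs to study treatment will be tabulated for all subjects combined and by treatment". Protocol 12.4 is narrower: "The incidence and severity of AEs reported during the study and their relationship to study drug will be tabulated". None of these names duration, time to resolution or the number unresolved.

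The nearest general provision is in SAP section 6, General: "All measured variables and derived parameters will be listed individually and, if appropriate, tabulated by descriptive statistics".

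The data for a duration summary are collected. Protocol 5.1 records for each event the "description of the event, date and time of onset", and the matching date and time of resolution.

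Persistence also matters elsewhere in the protocol. In 11.2.4, one trigger for suspending enrollment is that more than 20% of subjects have a drug-related grade 3 event "for a period duration of more than 28 days after injection". In 2.2 and 11.1, an event unresolved at Day 84 leads to a further visit 6 to 8 weeks later.

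**The concern.** The trial compares two doses with placebo, and safety is a listed secondary endpoint. For an injected product whose main adverse effects are local reactions, tolerability depends on how often they occur, how bad they get and how long they last. The plan covers the first two.

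The sponsor's own background gives a reason to want the third. In the Phase 2a submental study (Protocol 1.2.4.1.4), bruising, induration, edema, pain and erythema were the commonest events, "all of which were reported with a similar incidence in the RZL-012 and placebo treatment groups". That study named duration beside frequency and severity among the attributes it assessed. In the abdominal Phase 2a study (1.2.4.1.2), one case at 180 mg was reported in which "erythema and edema were still observed up to Day 140".

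If reactions were about equally frequent in all arms here but lasted longer on active drug, or longer on the high dose than on the low dose, the named tables need not show it. The internal committee would not fill the gap, because it reviews the data blinded.

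**Working it through.** The plan states no figure on this point, so the check is mainly of text.

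**What each planned output can show**

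| Output | Source | Sees occurrence | Sees grade | Sees duration |
|---|---|---|---|---|
| Incidence by treatment | SAP 6; Protocol 12.4 | yes | no | no |
| Severity by treatment | SAP 6; Protocol 12.4 | yes | yes | no |
| Seriousness, relation | SAP 6 (relation also in Protocol 12.4) | yes | no | no |
| Individual listings | SAP 6, General | yes | yes | readable line by line, not summarised by arm |

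An edema lasting 1 day and one lasting 8 weeks, with the same peak grade, count the same in the incidence and severity tables.

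**What the earlier studies found**

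- *Submental study* (8 + 10 = 18 active, 4 + 6 = 10 placebo). Incidence of the common reactions was similar. Severity differed at high dose, with 3 subjects reporting severe edema and 2 severe induration. These were severe only in the first 24 hours, then moderate to mild, and had resolved by Day 56. Erythema and bruising were not dose related and had mostly resolved by Day 14.
- *Abdominal study*. Injection site pain and edema were more frequent on active treatment than on placebo. One case persisted to Day 140.

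So incidence separated drug from placebo in one study and severity did so in the other. After the first day, the milder phase of the submental reactions is distinguished mainly by its length.

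**Illustration.** The rates below are assumptions; only the 45 per arm comes from the documents. The 95% half-width is 1.96 × √[p₁(1−p₁)/45 + p₂(1−p₂)/45].

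| Measure | Active | Placebo | Difference (points) | Half-width (points) |
|---|---|---|---|---|
| Any occurrence | 90% | 90% | 0 | 12.4 |
| Lasting beyond a fixed day | 20% | 5% | 15 | 13.3 |
| Lasting beyond a fixed day | 30% | 10% | 20 | 16.0 |
| Lasting beyond a fixed day | 40% | 10% | 30 | 16.8 |

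Any of the last three rows can coexist with the first. Differences of this size can be estimated, roughly, at 45 per arm. If durations are alike, the true difference is zero and the extra table would be expected to show little.

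**Why a censoring rule is needed.** AE reporting ends at Day 84 (Protocol 11.1), with later contact only for some subjects. Suppose durations from injection are exponential with a median of 28 days. The share of affected subjects unresolved at Day 84 is then 0.5^(84/28) = 12.5%. With a median of 14 days it is 0.5^(84/14) = 1.6%. The means, standard deviations and medians in SAP section 6, General, have no place for an unfinished duration. Dropping those events would shorten the apparent duration most in the arm with the longest reactions.

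**The case against.** The best reply is that the gap is small and partly covered. The general sentence in SAP section 6 lists everything measured and allows derived parameters to be tabulated, and the dates are in the database, so a duration table could be produced at any time. Severity, which did separate the arms in the submental study, is tabulated by treatment. All of this stands. It means that no data are lost and that part of the local-reaction signal is already captured. But the general sentence is conditional. It defines no duration variable, names no events or cut-offs and gives no rule for unresolved events, so those choices would be left until after unblinding.

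A reader might go further and infer that incidence is already known to be uninformative for this drug, so that the tolerability comparison rests on an empty measure. The documents do not support that. The similar incidence comes from one 28-subject study with unblinded physicians, at 5 mg in 0.1 mL per site; this trial uses 0.15 mL per site with 5.1 or 7.5 mg. In the abdominal study incidence did separate the arms for pain and edema.

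A reader might also infer that similar incidence shows the vehicle itself to be irritant, or that reactions do last longer on RZL-012. No passage describes the vehicle that way, and no durations are given by arm. The suspension rule concerns severe drug-related events and is a monitoring rule, so it shows that persistence is of interest without committing anyone to an analysis.

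**Conclusion.** The omission is real in both documents. Incidence and severity tables will capture part of the local-reaction signal but may miss a difference between arms in how long reactions last. The documents themselves treat persistence as relevant, through the earlier study's assessments, the suspension rule and the visit after Day 84.

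The size cannot be derived from the documents. The figures above show only what could go unseen and how precisely it could be estimated. They rest on assumed rates, on 45 treated subjects per arm and, for the Day 84 calculation, on exponential durations.

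No primary or sample-size result is affected. This is a worthwhile and inexpensive addition to a descriptive secondary safety analysis. It does not mean that the planned safety tables are wrong or that a formal test of duration is required.

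**What to change.** In SAP section 6, Analysis of Safety, add for each treatment-area event listed in Protocol 5.1, by arm and descriptively:

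1. Kaplan-Meier time from onset to resolution, with events unresolved at last contact censored, giving the median and 95% CI.
2. The number and percentage of treated subjects whose event lasted more than 28 days, and the number and percentage whose event was still ongoing at Day 84. Give the high-dose minus placebo and low-dose minus placebo differences with 95% CIs.

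The first summary covers only subjects who had the event. The second uses all treated subjects as denominator and so carries the comparison between arms. The text should also say how repeated reports of the same event in one subject are joined, and how a subject who leaves with an unresolved event before the cut-off is counted. The 28-day and Day 84 marks are borrowed from the protocol as reporting landmarks only; nothing here changes the suspension rule or subject management.

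The cost is a short SAP paragraph and a few tables from dates already recorded, with no new assessment and no change in sample size. The safety profile may look less favourable than incidence and severity alone would suggest. The addition should be made before unblinding, so that events and cut-offs are not chosen after seeing the results.

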## **7. RELATED DOCUMENTS (OPTIONAL)**

Raziel Protocol \_RZL-012-SMF-P2BUS-001.6 , March 08 2022.

## **8. RELATED FORMS (OPTIONAL)**

Not Applicable

MediStat Statistics in Medicine	DOCUMENT NUMBER: 140-BST-PLN-001	PAGE: 16 of 16
TITLE: Statistical Analysis Plan of Protocol Number RZL-012-SMF-P2bUS-001	EFFECTIVE DATE : 08/03/2022 REVISION NUMBER : 1.0	

## **9. REFERENCES**

Not Applicable

## **10. APPENDICES**

Not Applicable
